### Dose Administration

The first 2 IP doses must be administered on-site. For further details during the COVID-19 pandemic please refer to [Appendix H](#).

IP will be administered by a qualified HCP (e.g. Pharmacist, or study nurse) at the site. The injection site must be recorded in the source documents at each treatment visit and in the eCRF. The person administering the dose will wipe the skin surface of the upper arm, anterior thigh or abdomen with alcohol and allow to air dry. The skin will be pinched to isolate the SC tissue from the muscle. The needle will be inserted at a 90 degree angle approximately halfway into the SC tissue. The IP will be slowly injected (at least 5 second duration is recommended) into the SC tissue using gentle pressure. The area should not be massaged after injection. It is advised that the site of injection of IP be rotated such that the subject receives IP at a different anatomical site at each treatment visit. Injection site must be documented on the eCRF and in the source documents at each treatment visit. In cases when rotation of the injection site is not feasible and/or the subject prefers not to rotate injection sites, the reason for not rotating the injection site should be documented in the source documents. The suggested injection site rotation sequence is presented below in [Figure 2](#).

**Figure 2 Suggested Schema of Rotation of Injection Sites**

Subjects should be observed for a minimum of 2 hours after administration of the first two IP administrations, in the DESTINATION Study for the appearance of any acute drug reactions. For the remaining doses, subjects will be observed for a minimum of 1 hour after IP administration for any such reaction.

If any of the following should occur, the IP should not be administered:

- The subject received allergen immunotherapy injection on the same day as scheduled IP administration.
- The subject has an intercurrent illness that in the opinion of the investigator and/or medical monitor may compromise the safety of the subject in the study (e.g., viral illnesses).
- The subject is febrile ( $\geq 38^{\circ}\text{C}$ ;  $\geq 100.4^{\circ}\text{F}$ ) within 72 hours prior to IP administration.

The visit should be rescheduled within the allowed visit window and IP should be administered at that visit. If this is not possible the IP administration should be skipped. If a subject skips 2 consecutive IP administrations, the AstraZeneca Study Physician should be contacted to discuss further participation.

If the subject reports an injection site reaction, the investigator or qualified designee will complete the AE eCRF page.

**6.3 Measures to minimise bias: randomisation and blinding**

The Investigator(s) will:

1. Obtain signed informed consent or assent from the potential subject, or their guardian/legal representative, before any study specific procedures are performed.
2. Assign the potential subject a unique enrolment number (which begins with an CCI via the Interactive Response Technology (IRT).
3. Determine subject eligibility.
4. Assign the eligible subject unique randomization code via the Interactive Response Technology (IRT).

Tezepelumab - D5180C00018

5. All subjects will be randomized in the LTE study to maintain the blinding. Subjects randomized to placebo in the predecessor studies will be randomized in a 1:1 ratio (tezepelumab:placebo) stratified by predecessor study. Subjects randomized to tezepelumab in the predecessor studies will be assigned and continue with tezepelumab in the LTE study. Randomization numbers will be grouped in blocks. If a subject withdraws from the study, then his/her enrolment/randomization code cannot be reused. Withdrawn subjects will not be replaced.

Specific information concerning the use of the IRT will be provided in a separate manual.

### **Procedures for handling incorrectly enrolled or randomized subjects**

Subjects who fail to meet the eligibility criteria should not, under any circumstances, be randomized or receive study medication. There can be no exceptions to this rule. Subjects who are enrolled, but subsequently found not to meet all the eligibility criteria must not be randomized or initiated on treatment and must be withdrawn from the study.

Where a subject does not meet all the eligibility criteria but is randomized in error, or incorrectly started on treatment, the Investigator should inform the AstraZeneca Study Physician immediately, and a discussion should occur between the AstraZeneca Study Physician and the investigator regarding whether to continue or discontinue the subject from treatment. Study treatment must be discontinued in all cases where continued treatment is deemed to pose a safety risk to the subject and AstraZeneca Study Physician must ensure the decision is appropriately documented. Subjects that are discontinued from treatment should be followed up according to the options described in section 7.1.1.

In those cases where continuation of the study therapy is judged not to present a concern related to safety and disease management, the rationale for continuing study therapy must be clearly documented.

### **Methods for assigning treatment groups**

All subjects will be centrally assigned to randomized study treatment using an interactive response technology (IRT). Randomization codes will be assigned strictly sequentially in each stratum as subjects become eligible for randomization. Randomization will be stratified by predecessor study.

All subjects will be re-randomized in this study, and will be assigned to treatment according to the following algorithm:

- \* Subjects previously randomized with blinded tezepelumab will be assigned and stay on blinded tezepelumab
- \* Subjects previously randomized to blinded placebo will be randomized 1:1 to blinded

Tezepelumab - D5180C00018  
tezepelumab or placebo.

The randomization list will be prepared by a computerized system provided by Calyx Clinical Research Solutions on behalf of AstraZeneca (AZRand).

### **Ensuring blinding**

This study is a double-blind study in which tezepelumab and placebo are not visually distinct from each other. All packaging and labelling of IP will be done in such way as to ensure blinding for all sponsor and investigational site staff. Neither the subject nor any of the investigators or sponsor staff who are involved in the treatment or clinical evaluation and monitoring of the subjects will be aware of the treatment received. Since tezepelumab and placebo are not visually distinct, IP will be handled by a qualified person (e.g., pharmacist or study nurse) at the site. Although the study will initially be completely double-blind (i.e., blind for subjects, Investigators/site staff, and Sponsor/designated CRO), at the conclusion of the Phase 3 Studies D5180C00007 or D5180C00009 treatment allocation for subjects may become known to the Sponsor staff and/or designated CRO. The blind will be maintained for the Investigator, investigational site staff, and for the subject. To prevent complete unblinding of this study, treatment-revealing information will not be shared with the study sites or subjects (subject-level listings, as well as other treatment-revealing information will be redacted from the Clinical Study Reports). Further details are provided in a separate Blinding Plan.

An AstraZeneca site monitor will perform IP accountability. In the event that the treatment allocation for a subject becomes known to the investigator or other study staff involved in the management of study subjects or needs to be known to treat an individual subject for an AE, the sponsor must be notified immediately by the investigator and, if possible, before unblinding.

The following personnel will have access to the randomization list:

- Those carrying out the packaging and labelling of IP
- Those generating the randomization list
- Personnel at the IRT company
- Supply Chain Management department
- Patient Safety department at AstraZeneca
- CCI
- Those involved in the reporting and reviewing the DSMB presentations

Tezepelumab - D5180C00018

No other member of the extended study team at AstraZeneca, or any CRO handling data, will have access to the randomization scheme during the conduct of the study until planned unblinding at primary database lock at Week 104.

The information in the randomization list will be kept from other personnel involved in the conduct of the study and in a secure location until the end of the study. Further details are provided in a separate Blinding Plan.

### **Methods for unblinding**

Individual treatment codes, indicating the treatment randomization for each randomized subject, will be available to the Investigator(s) and delegate(s) at the study sites from the IRT. Routines for this will be described in the IRT user manual that will be provided to each site.

The treatment code should not be broken except in medical emergencies when the appropriate management of the subject requires knowledge of the treatment randomization. The Investigator should document and report the action to AstraZeneca, without revealing the treatment given to subject to the AstraZeneca staff.

AstraZeneca retains the right to break the code for SAEs that are unexpected and are suspected to be causally related to an IP and that potentially require expedited reporting to regulatory authorities. Treatment codes will not be broken for the planned analyses of data until all decisions on the evaluability of the data from each individual subject have been made and documented. Further details are provided in a separate Blinding Plan.

## **6.4 Treatment compliance**

Any change from the dosing schedule or dose discontinuations should be recorded in the eCRF. The IP Storage Manager is responsible for managing the IP from receipt by the study site until the destruction or return of all unused IP. The date and time of all IP administrations, as well as any missed doses, should be recorded in the appropriate section of the eCRF.

## **6.5 Concomitant therapy**

All subjects will be taking medium- or high-dose ICS and potentially at least one additional asthma controller medication (including LABA, Leukotriene modifiers, theophylline, cromones). Additionally, the subject may be taking OCS for the treatment of asthma.

During the study, subjects may use an inhaled short-acting bronchodilator as needed as a reliever or rescue medication due to worsening of asthma.

Maintenance regimen of allergen-specific immunotherapy is allowed but should not be administered on the same day as investigational product.

Tezepelumab - D5180C00018

Investigators may prescribe concomitant medications or treatments to provide adequate supportive care as deemed necessary, except for those medications identified as “excluded” in Prohibited medications. See [Table 7](#).

Maintenance asthma medication is not regarded as an IP but will be provided/reimbursed by AstraZeneca according to local regulations in order to maintain appropriate oversight and access to this concomitant therapy. Any marketed (e.g. omalizumab, mepolizumab, reslizumab, etc.) or to be marketed or investigational biologic treatment will not be provided/reimbursed by AstraZeneca.

Any medication or vaccine including over-the-counter or prescription medicines, vitamins, and/or herbal supplements that the subject is receiving at the time of enrolment or receives during the study must be recorded along with:

- Reason for use
- Dates of administration including start and end dates

All concomitant medication should be documented in the source and recorded in the eCRF.

**Table 6 Restricted Medications**

Medication/class of drug:	Usage
Short-acting beta-agonists (SABA)	Regular scheduled use of SABA is not allowed from V1 and throughout the IP treatment and preferably 4 weeks after the last dose of IP, PRN use is allowed if needed, however attention should be paid to the following restrictions.  SABA should be withheld for at least 6 hours prior to scheduled CCI at site with the exception of any unscheduled visits due to asthma worsening.
Maintenance treatment with ICS and long-acting bronchodilators (including ICS/LABA combinations)	The subject should be instructed not to take their usual asthma controller medication (i.e., LABA) prior to scheduled ECG assessment (please refer below for long-acting bronchodilator restrictions). Use of SABA should be avoided within 6 hours before ECG assessments. The medication restrictions are waived for the screening ECG at Visit 1.  Twice daily bronchodilators should be withheld for at least 12 hours prior to the scheduled CCI at site.  Once daily bronchodilators should be withheld for at least 24 hours prior to the scheduled CCI at site.  Subjects will not need a washout of their asthma medications for unscheduled visits due to asthma worsening.

Tezepelumab - D5180C00018

Medication/class of drug:	Usage
Additional Maintenance Controllers	
Once daily LABA and LAMA should be withheld for at least 24 hours prior scheduled CCI [REDACTED] at site visits with the exception of any unscheduled visits due to asthma worsening.
 
Twice daily LABA or LAMA containing therapies should be withheld for at least 12 hours prior to scheduled CCI [REDACTED] at site with the exception of any unscheduled visits due to asthma worsening.
 
LTRA should be restricted for at least 24 hours prior to scheduled CCI [REDACTED] at site with the exception of any unscheduled visits due to asthma worsening.
 
Twice daily theophyllines should be withheld for at least 12 hours prior to scheduled CCI [REDACTED] at site with the exception of any unscheduled visits due to asthma worsening.
 
Once daily theophyllines should be withheld for at least 24 hours prior to scheduled CCI [REDACTED] at site with the exception of any unscheduled visits due to asthma worsening.

Short-acting anticholinergics (e.g. ipratropium)	These are not allowed as a rescue treatment for worsening asthma symptoms from V1 and throughout the IP treatment and preferably 4 weeks after the last dose of IP. They may be used for managing an asthma exacerbation event.
Inactive/killed vaccinations (e.g. inactive influenza)	Allowed provided they are not administered within 5 days before or after any IP dosing visit.
COVID-19 vaccinations	Refer to section 6.5.5 and 8.2.6
Allergen Immunotherapy	
Allowed, if on stable therapy for at least 2 months prior to date of Visit 1 with no anticipated change during the treatment period.
 
These should not be administered on the same day as IP administration.

**Table 7 Prohibited Medications**

Prohibited medication/class of drug:	Usage
Live Attenuated Vaccines	Not allowed during the study up to Week 116.

Tezepelumab - D5180C00018

Prohibited medication/class of drug:	Usage
Any immunomodulators or immunosuppressives (corticosteroids with systemic effects such as oral, parenteral, or intra-articular administration for reasons other than asthma are not allowed. However, corticosteroid treatment of adrenal insufficiency is allowed.)	Not allowed throughout the IP treatment period and preferably 4 weeks after the last dose of IP.
Immunoglobulin or blood products	Not allowed throughout the IP treatment period and preferably 4 weeks after the last dose of IP.
Any marketed (e.g. omalizumab, mepolizumab, reslizumab, etc.) or to be marketed biologic treatment	Not allowed throughout the IP treatment period (even if the subject has discontinued IP and continues with rest of the study visit till end of study) and until the week 116.  Please note: Biologics should only be introduced after Week 116, in the presence of evidence of asthma deterioration.
Other investigational products (including investigational use of an approved drug)	Not allowed throughout the IP treatment period (even if the subject has discontinued IP and continues with rest of the study visit till end of study) CCI XXXXXXXXXX CCI XXXXXXXXXX
Chronic use of oral corticosteroids in diseases other than asthma.	Not allowed throughout the IP treatment period and preferably 4 weeks after the last dose of IP.

### 6.5.1 Asthma Background Medication

If the subject's symptoms are stable, as per investigator's judgement, attempts to reduce background asthma medications can be made every 3 months starting from Visit 1 throughout the study as per Appendix F 1, Figure 4, if thought appropriate by the investigator.

In the event the subject experiences worsening of asthma symptoms due to the reduction of background asthma medications, guidance is provided in Appendix F 2, Figure 5 to step up the background asthma medications, as per investigator discretion, at 3 monthly intervals.

In the event a subject experience an exacerbation of asthma, this should be treated appropriately as per investigator discretion.

### 6.5.2 Other concomitant treatment

Tezepelumab - D5180C00018

Other medication other than that described above, which is considered necessary for the subject's safety and wellbeing, may be given at the discretion of the Investigator and recorded in the appropriate sections of the Case Report Form.

### 6.5.3 Rescue medication

SABA should be withheld for at least 6 hours prior to scheduled site visit CCI at site with the exception of any unscheduled visits due to asthma worsening.

Albuterol (US)/salbutamol (ex US) rescue medication will be provided by the sponsor and obtained locally. Rescue use of SABA administered via nebulization is discouraged, except as urgent treatment during an asthma exacerbation.

### 6.5.4 Bronchial Thermoplasty

Subjects should not be treated with bronchial thermoplasty during the study.

### 6.5.5 COVID-19 Vaccination

If COVID-19 vaccination is in the best interest of the subject it is recommended that for subjects in study treatment phase IP should not to be administered within 14 days before, or 28 days after a dose of vaccine. In case of subjects in follow up phase it is advised that vaccination should not occur within 14 days after the last IP dose. As those intervals might change, please discuss with the Study Physician. For details, refer to section 8.2.6.

## 6.6 Dose modification

N/A

## 6.7 Treatment after the end of the study

Subjects who complete follow-up at week 116 CCI should be given standard of care at the discretion of the investigator.

# 7 Discontinuation of treatment and subject Withdrawal

## 7.1 Discontinuation of study treatment

Subjects may be prematurely discontinued from investigational product (IP) in the following situations:

Note that discontinuation from study treatment is NOT the same thing as a complete withdrawal from the study

- Subject decision. The subject is at any time free to prematurely discontinue treatment, without prejudice to further treatment
- An adverse event considered to jeopardise the safety of a subject participating in the study

Tezepelumab - D5180C00018

- Pregnancy
- Severe non-compliance with the Clinical Study Protocol
- Development of any study specific criteria for premature discontinuation of IP, including:
  - An anaphylactic reaction to the IP requiring administration of epinephrine
  - A helminth parasitic infestation requiring hospitalization
  - An asthma-related event requiring intubation
  - Any malignancy, except subjects who develop basal cell carcinoma or localized squamous cell carcinoma of the skin, provided that the malignancy is excised and determined to have clean margins.
- Development of one or more of the following:
  - Confirmed ALT or AST increase of  $\geq 8$  x ULN
  - Confirmed ALT or AST increase of  $\geq 5$  x ULN for more than 2 weeks
  - Confirmed ALT or AST increase of  $\geq 3$  x ULN and total bilirubin of  $\geq 2$  x ULN
  - ALT or AST of  $\geq 3$  x ULN with the appearance of fatigue, nausea, vomiting, right upper quadrant pain or tenderness, fever, rash and/or eosinophilia ( $\geq 5\%$ )

Before a decision to prematurely discontinue a subject from IP is instituted, the AstraZeneca Study Physician should be consulted regardless of the reason for discontinuation.

See the [Schedule of Activities \(SoA\)](#) for data to be collected at the time of premature treatment discontinuation and follow-up and for any further evaluations that need to be completed.

If a subject prematurely discontinues IP due to a study specific discontinuation criterion, this should always be recorded as 'Development of study specific withdrawal' on the Discontinuation of Investigation Product form in the eCRF.

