## Tezepelumab - D5180C00018

Cessation of contraception after this point should be discussed with a responsible physician. Periodic abstinence, the rhythm method, and the withdrawal method are not acceptable methods of contraception.

Adolescent specific recommendations: If subject is female and has reached menarche or has reached Tanner stage 3 breast development (even if not having reached menarche), the subject will be considered a female of child bearing potential.

A highly effective method of contraception is defined as one that results in a low failure rate (i.e., less than 1% per year) when used consistently and correctly. Highly effective forms of birth control include: true sexual abstinence, a vasectomised sexual partner, Implanon™, female sterilization by tubal occlusion, any effective intrauterine device/system (IUD/IUS), Depo-Provera™ injections, oral contraceptive, and Evra Patch™ or Nuvaring™. WOCBP must agree to use highly effective method of birth control, as defined above, from enrolment (Visit 1), throughout the study duration and within 16 weeks after last dose of investigational product (IP), and have a negative urine pregnancy test result at Visit 1.

Women not of childbearing potential are defined as women who are either permanently sterilized (hysterectomy, bilateral oophorectomy, or bilateral salpingectomy), or who are postmenopausal. Women will be considered postmenopausal if they have been amenorrheic for 12 months prior to the planned date of randomization without an alternative medical cause. The following age specific requirements apply:

- o Women <50 years old would be considered postmenopausal if they have been amenorrheic for 12 months or more following cessation of exogenous hormonal treatment and follicle stimulating hormone (FSH) levels in the postmenopausal range.
- o Women ≥50 years old would be considered postmenopausal if they have been amenorrheic for 12 months or more following cessation of all exogenous hormonal treatment.

4. Inclusion criterion #4 removed with version 2.0 of the clinical study protocol.

5. **Inclusion criteria at randomization:** Female or male subjects who have not met investigational product discontinuation criteria and have attended the EOT visit in either study D5180C00007 or D5180C00009. Subjects with inadequate compliance with investigational product, assessed at the discretion of the sponsor, might not be randomized.

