## 8 Study Assessments and Procedures

Tezepelumab - D5180C00018

Study procedures and their timing are summarized in the [Schedule of Activities \(SoA\)](#).

The investigator will ensure that data are recorded on the electronic Case Report Forms. The Web Based Data Capture (WBDC) system will be used for data collection and query handling.

The investigator ensures the accuracy, completeness, legibility and timeliness of the data recorded and of the provision of answers to data queries according to the Clinical Study Agreement. The investigator will sign the completed electronic Case Report Forms. A copy of the completed electronic Case Report Forms will be archived at the study site. Additional data will be collected to assess the impact of COVID-19.

Immediate safety concerns should be discussed with the Sponsor immediately upon occurrence or awareness to determine if the subject should continue or prematurely discontinue Study treatment.

Adherence to the study design requirements, including those specified in the [Schedule of Activities \(SoA\)](#), is essential and required for study conduct.

Procedures conducted as part of the subject's routine clinical management (e.g., blood count) and obtained before signing of the ICF may be utilized for screening or baseline purposes provided the procedures met the protocol-specified criteria and were performed within the time frame defined in the [Schedule of Activities \(SoA\)](#).

The maximum amount of blood collected from each subject over the duration of the study will be approximately 100 mL, including any extra assessments that may be required, will not exceed 150 mL. Repeat or unscheduled samples may be taken for safety reasons or for technical issues with the samples. CCI

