**Figure 3 COVID-19 Vaccination Between IP Dosing**Reporting of COVID-19 Vaccination in eCRF

COVID-19 vaccine details including vaccine's name/manufacturer, route of administration, and vaccination date should be entered into the eCRF CM module.

If a subject has experienced an AE/SAE associated with COVID-19 vaccination, the investigator should record this in the source documentation and determine whether the IP should be continued, skipped or permanently discontinued in accordance with section 7.1.

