##### **8.4.2.1 Maternal exposure**

If a subject becomes pregnant during the course of the study, investigational product should be discontinued immediately.

Pregnancy itself is not regarded as an adverse event unless there is a suspicion that the investigational product under study may have interfered with the effectiveness of a contraceptive medication. Congenital anomalies/birth defects and spontaneous miscarriages should be reported and handled as SAEs. Elective abortions without complications should not be handled as AEs.

Tezepelumab - D5180C00018

The outcome of all pregnancies (spontaneous miscarriage, elective termination, ectopic pregnancy, normal birth or congenital anomalies) should be followed up and documented even if the subject was discontinued from the study.

If any pregnancy occurs in the course of the study, then the Investigator or other site personnel informs the appropriate AstraZeneca representatives within 1 day i.e., immediately but **no later than 24 hours** of when he or she becomes aware of it.

The designated AstraZeneca representative works with the Investigator to ensure that all relevant information is provided to the AstraZeneca Subject Safety data entry site within 1 or 5 calendar days for SAEs (see Section 8.4.1) and within 30 days for all other pregnancies.

The same timelines apply when outcome information is available.

The PREGREP module in the CRF is used to report the pregnancy and the PREGOUT is used to report the outcome of the pregnancy.

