2.2 Violations and deviations

Important protocol deviations (PDs) will be listed and tabulated in the Clinical Study Report (CSR) only for randomised subjects. These are defined as PDs which may significantly affect the completeness, accuracy and/or reliability of the study data, or which may significantly affect a subject's rights, safety, or well-being. Important PDs in this study will be grouped under one of the following categories (refer to Protocol Deviation Plan):

- Did not fulfil key eligibility criteria
- Developed discontinuation criteria during the LTE study but continued IP
- Received prohibited concomitant medication during the LTE study

- Did not comply with restrictions during the study
- IP management issues

All important PDs, except Code 10.9 receiving wrong IP kit number and Code 10.22 IP dose in excess of 700 mg administered within a 2-week period, will be identified and documented by the study team prior to unblinding of the LTE study. As far as possible, the occurrence of important PDs will be monitored (blinded) during the study, with the emphasis on their future prevention.

The study PD Plan outlines the management of PDs and includes the proposed specific categories of PDs in this study. Any PDs which are not defined as important or COVID-19 related will not be reported and discussed in the CSR.

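### Protocol 7.1 allows but does not require stopping IP for its four study-specific criteria, while SAP 2.2 counts continuing IP after discontinuation criteria as an important deviation

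*Protocol*

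**What the plan says.** Protocol 7.1 opens: "Subjects may be prematurely discontinued from investigational product (IP) in the following situations". The list beneath covers subject decision, adverse events that endanger the subject, pregnancy, severe non-compliance, four study-specific criteria and four liver criteria. The study-specific criteria are anaphylaxis to IP treated with epinephrine, helminth infestation leading to hospitalization, an asthma event leading to intubation, and malignancy. Malignancy excepts basal cell and localized squamous cell skin cancers excised with clean margins. Before any decision to stop, "the AstraZeneca Study Physician should be consulted regardless of the reason for discontinuation".

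Other text bears on whether the criteria bind:

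- SAP 2.2 lists among its important protocol deviations: "Developed discontinuation criteria during the LTE study but continued IP".
- Protocol 5.1, inclusion 5, admits "Female or male subjects who have not met investigational product discontinuation criteria".
- Protocol 8.4.2.1 is directive for pregnancy: "investigational product should be discontinued immediately".
- Protocol 8 says, with regard to IP: "Immediate safety concerns should be discussed with the Sponsor immediately upon occurrence or awareness to determine if the subject should continue or prematurely discontinue".
- Protocol 8.2.6, for events after COVID-19 vaccination, asks the investigator to "determine whether the IP should be continued, skipped or permanently discontinued in accordance with section 7.1".

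**The concern.** One permissive verb does two jobs. For subject decision or non-compliance, discretion is what one would want. For the four study-specific criteria it leaves re-dosing open after events that the plan itself labels as criteria for stopping.

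Two things are at stake. The first is safety: taken literally, 7.1 lets a subject who had anaphylaxis to IP and needed epinephrine receive the next dose. The second is consistency across roughly 350 sites. After the same event one site may stop and another continue. The first records an adverse event leading to discontinuation (DAE); the second does not, and may be recorded as an important deviation although it acted within the wording of 7.1. DAEs are a core summary for the primary objective of long-term safety and tolerability.

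**Working it through.** The point is mainly textual. The arithmetic only gives scale.

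**Is a required stop stated anywhere else for the four criteria?**

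- Protocol 8.4.5 and Appendix E (anaphylaxis) cover recognition, treatment and tryptase sampling. Neither says to stop IP.
- Appendix D (liver) covers identification, reporting and review; D 1 refers liver management back to 7.1.
- Protocol 8.2.6 also refers back to 7.1, and Protocol 8 calls for a discussion, not a stop.
- Protocol 6.3 has mandatory wording, but only for subjects randomized or started in error.
- Protocol 6.2 bars a dose after fever within 72 hours or on the day of allergen immunotherapy. Its intercurrent-illness limb depends on the investigator's or medical monitor's opinion. Fever thus triggers a firmer instruction than earlier anaphylaxis to the product.

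So no operative sentence requires the stop.

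**Does other text assume that the criteria bind?**

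- SAP 2.2: continuing after developing discontinuation criteria is an important deviation. This is direct evidence.
- The skin-cancer exception: an exemption has little purpose if the criterion is optional. The protocol's version history (Version 2.0) gives as its rationale that these subjects can stay on treatment, which implies that others with malignancy cannot.
- Inclusion 5: indirect only, because it concerns criteria met in the predecessor studies.

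**Scale of one inconsistent decision in the primary safety group (Randomised Tezepelumab, SAF)**

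- Inputs: 860 and 115 expected rollovers, 90% completing dosing and 90% of those continuing (Protocol 1.2). The stated 3:1 overall ratio after a 1:1 split of placebo implies equal predecessor arms: if T + P/2 = 3 × P/2, then T = P.
- D5180C00007: 860 / (0.9 × 0.9) = 1,062; half is 531; 1/531 = 0.19 percentage points.
- D5180C00009: 115 / 0.81 = 142; half is 71; 1/71 = 1.4 percentage points.

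**Scale of one extra dose on on-treatment exposure (SAP 3.1.5)**

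- Each dose moves the end of the on-treatment window by 28 days: 28 / 365.25 = 0.077 subject-years.
- A full window runs from the first dose to Week 100 plus 33 days: 700 + 33 + 1 = 734 days. One dose is 28/734 = 3.8% of one subject's window.
- At group level, take 860/2 = 430 continuing-tezepelumab subjects from D5180C00007, all completing: 430 × 734 / 365.25 = 864 subject-years, and 0.077/864 = 0.009%.

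**Analyses essentially unaffected**

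- AAER: the planned-treatment analysis keeps follow-up after IP stops (SAP 3.3.1.1 and 4.6.1).
- On-study adverse events: the window does not depend on the last dose.
- The dropout-reason imputation (DRMI): SAP Table 6 sends both an adverse event and a study-specific criterion to placebo.

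**The case against.** The strongest reply is that the intent is clear. 7.1 calls these criteria for premature discontinuation and gives them their own eCRF reason, SAP 2.2 treats continuing as a deviation, and *may* simply introduces a list that must also cover subject decision. Safeguards exist too. Safety concerns go to the sponsor at once (Protocol 8), serious events are reported within 24 hours (8.4.1), anaphylaxis is defined as serious (8.4.5), and hospitalization for helminth infestation meets the SAE definition (Appendix B 2). Dosing is every four weeks by a health professional, who can withhold a dose under 6.2 without prior consultation.

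Much of this stands. The safeguards make divergence between sites less likely, and most investigators would probably stop. But they provide contact and discussion, not a rule. A clear intent is a reason to write it down: the SAP is not an instruction to sites.

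A reader might go further and infer that the three confirmed liver thresholds should also carry a mandatory permanent stop because the plan treats them as binding. The documents do not support that. Inclusion 5 looks back to the predecessor studies, the skin-cancer exception concerns malignancy only, and whether SAP 2.2 reaches the liver thresholds depends on the Protocol Deviation Plan, which is not available. Appendix D 5 provides a review for alternative explanations when transaminases and bilirubin are both raised; an immediate permanent stop would pre-empt it. A subject whose enzymes rose from, say, viral hepatitis would lose IP and, under 7.1.1, could have no other biologic until Week 116. The fourth liver criterion, ALT or AST at least 3 × ULN "with the appearance of fatigue, nausea, vomiting, right upper quadrant pain or tenderness, fever, rash and/or eosinophilia", suits a mandatory stop even less. It is not marked as confirmed, and eosinophil counts are redacted from central reports, although 8.2.1.2 lets an investigator order one for safety.

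**Conclusion.** The point holds for the four study-specific criteria. Protocol 7.1 permits a stop that nothing else requires, and it is at odds with the SAP's deviation category and with the logic of the malignancy exception. For the liver thresholds no internal contradiction is shown, and stricter wording there is a trade-off.

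A reader might also infer that the trial's results are at risk. They are not, to any useful degree. One decision is worth about 0.19 or 1.4 DAE percentage points in the primary group, and one extra dose about 0.009% of exposure in the larger study's continuing group. These figures assume equal predecessor arms and the protocol's 90% × 90% rollover; the exposure share also assumes full completion. How many subjects would meet a criterion cannot be derived from the documents. The change is worth making for patient safety and for consistent DAE and deviation classification.

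**What to change.** In Protocol 7.1, split the list:

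- **Must be discontinued:** the four study-specific criteria, and pregnancy to match 8.4.2.1. The Study Physician is informed, but the stop does not wait for consultation.
- **May be discontinued:** subject decision, other adverse events and severe non-compliance, as now.
- **Liver thresholds:** at most, withhold IP when a threshold is met and decide on permanent discontinuation after the Study Physician and Appendix D review.

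In SAP 2.2, tie the deviation category to the mandatory list, so that only continuing against an explicit instruction counts.

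The cost is wording in two places and a small loss of investigator discretion. A liver hold could mean a skipped dose if it outlasts the ±5-day visit window. A subject who must stop also comes under the existing bar on other biologics until Week 116, as anyone who stops already does. Judgement remains over whether a reaction was to IP or an event was asthma-related. No sample size, endpoint or blinding arrangement changes.
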